9.7.4. Open-Label or Double-Blind Active-Controlled Treatment Period (Month 12 to Month 18)

9.7.4.1. Month 12 (± 7 days)

Subjects will bring a urine sample that was collected at home (all voids from midnight the night before to the first morning void after awakening for the day) as specified in [Section 9.3.3](#). Subjects should arrive at the study site for the Month 12 visit in the morning in a fasted state (minimum 8-hour fast) and prior to their morning dose of glucocorticoid and study drug. They should bring their morning dose of glucocorticoid and study drug to take at the study site after the first set of blood samples.

The following study procedures and assessments will be performed:

- Perform a physical examination including measurement of waist circumference.
- Perform vital signs (including weight).
- Collect blood samples for TSH and free T4; chemistry, hematology, and coagulation labs; PK; hormone panel (prior to and approximately 2 hours after morning dose of glucocorticoid); fasting metabolic panel; bone markers.
- Perform glucose tolerance test (only in subjects without diabetes mellitus).
- Collect urine sample for urinalysis; urine NTx (fasting, after first morning void); urine pregnancy test (only for female subjects of childbearing potential).
- Collect subject's at-home urine sample.
- Perform 12-lead ECG.
- Perform testicular ultrasound (males only).
- Perform DXA for assessment of bone mineral density and body composition.
- Administer the SF-36; the EQ-5D-5L; the MAF; the MOS-12; the PGWBI; the BPRS; the C-SSRS (Since Last Visit version).
- Administer the Hirsutism and Acne Scales (female subjects only); review the Menstrual Cycle Questionnaire (only in female subjects of childbearing potential who are not on hormonal or intrauterine device contraceptives).
- Dispense study drug.
- Study drug accountability.
- Record concomitant medications.
- AE monitoring.

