## 6.8. Handling of Missing Data

### 6.8.1. Start Dates for Adverse Events

For the purpose of estimating the time of the event in relationship to study drug (ie, study day), missing and incomplete (“partial”) dates for AEs will be imputed using the following algorithm. For start dates that are missing day and month: impute 1st January, unless the year is the same as the first dose of study drug, in which case the start date will be imputed to the date of first dose of study drug. For start dates that are missing day alone: impute to the 1st of the month unless the month and year are the same as the first dose of study drug, in which case the start date will be imputed to the date of first dose of study drug. There will be no imputation for AE stop dates.

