### 11.2. Adverse Events

A treatment-emergent adverse event (TEAE) is an AE not present prior to the initiation of study drug dosing, or is an already present event that worsens either in intensity or frequency following the initiation of study drug dosing with an onset on or before the last dose of study drug + 28 days (to account for the study drug washout period).

TEAEs will be further defined for the two treatment periods. For the DB period, Investigators will be asked to respond “Yes” or “No” on the eCRF as to whether the AE started after the subject took the first dose of study drug. An AE with a response of “Yes” and that occurs on or before the last dose of study drug in the DB period will be classified as a TEAE for the DB period. If the subject’s last dose on study occurs in the DB period, then any AE occurring prior to the last dose of study drug in the DB period + 28 days will be considered a TEAE. If the investigator’s response is missing, then the treatment emergent status will be derived based on the AE onset date relative to the date of the subject’s first dose of study drug in the DB period or first dose of study drug in the OL period. If the AE onset date is unknown, it will be assumed that the AE is a TEAE and will be reported in the DB period TEAE summaries.

For the OL period, TEAEs will be defined as AEs starting after the first dose of study drug in the OL period and prior to the last dose of study drug in the OL period. If the subject’s last dose on study occurs in the OL period, then any AE occurring prior to the last dose of study drug in the OL period + 28 days will be considered a TEAE.

Adverse events with an onset date after the last dose of study drug + 28 days will not be considered treatment emergent (non-TEAEs).

The following TEAE summaries will be produced for the DB period (Day 1 up to Week 24) and for the 6-month OL period (Week 24 to Month 12) separately:

TEAEs categorized by MedDRA system organ class (SOC) and/or preferred term (PT) will be summarized in frequency tables. The frequency tables will include the number and percentage of unique subjects experiencing each event one or more times by treatment group.

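### The TEAE period rules in SAP 11.2 do not adjoin, so a few treatment-emergent onset dates fall in neither the double-blind nor the open-label table

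*SAP*

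**What the plan says.** SAP 11.2 opens with a general definition: an event that is new or worse after dosing begins, "with an onset on or before the last dose of study drug + 28 days". Only later onsets are non-TEAEs. It then sets period rules, and the TEAE tables are produced for the two periods separately:

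- **DB:** an event with an investigator response of Yes "that occurs on or before the last dose of study drug in the DB period will be classified as a TEAE for the DB period".
- **OL:** "AEs starting after the first dose of study drug in the OL period and prior to the last dose of study drug" in that period.
- **Tail:** if the last dose on study falls in OL, "any AE occurring prior to the last dose of study drug in the OL period + 28 days will be considered a TEAE". A parallel sentence covers DB.
- **Response missing:** "treatment emergent status will be derived based on the AE onset date relative to the date" of the first DB or first OL dose.

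For an onset with only the day missing, SAP 6.8.1 defaults to day 1 of the recorded calendar month, with one exception: "unless the month and year are the same as the first dose of study drug, in which case the start date will be imputed". The value used in that exception is the first-dose date. SAP 6.7 equates the first dose with Day 1, so the month of OL start has no equivalent protection.

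On timing, Protocol 7 starts OL drug on the evening of the Week 24 visit, and Protocol 9.7.2.3.3 has that morning's dose taken on site. Protocol 9.7.4.1 says of Month 12: "They should bring their morning dose of glucocorticoid and study drug to take at the study site after the first set of blood samples". Protocol 11.2 asks for dates of onset and names no time of day.

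**The concern.** The DB rule is inclusive at its upper end. The OL rule is strict at both ends. The tails are strict where the general definition is inclusive. A date that lies between these bounds belongs to a TEAE by definition, but to no TEAE table. It is not in the non-TEAE table either, because that is reserved for onsets later than last dose + 28 days. The tables for SAEs, drug discontinuation, acute adrenal insufficiency and stress dosing are split by period in the same way.

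The dates affected are not arbitrary. Month 12 has a physical examination, ECG, laboratory tests, BPRS and C-SSRS, so findings tend to be dated that day. A late OL start may follow a dosing interruption. The partial-date rule raises a different problem, attribution: an event on open-label crinecerfont in a former placebo subject can be tabulated under placebo.

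**Working it through.** The plan states no figure to reproduce. The check applies the rules as written to each onset day.

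**Inputs.** Target Day 168 for Week 24 and Day 336 for Month 12 (SAP Table 4), so the OL period has 336 − 168 = 168 days (169 to 336). Onset is compared by date.

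**Rules as inequalities.** DB: onset ≤ last DB dose. OL: onset > first OL dose and < last OL dose. Tail: onset < last dose + 28.

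| Case (response Yes) | Dates in no TEAE table |
|---|---|
| On schedule, continues past Month 12 | 336 |
| First OL dose 1 day late, continues | 169, 336 |
| First OL dose 3 days late, continues | 169–171, 336 |
| First OL dose 7 days late, continues | 169–175, 336 |
| Last dose on study is OL Day 336 | 364 only (336 + 28) |
| Last dose on study is OL Day 250 | 278 only (250 + 28) |
| Last dose on study is DB Day 100 | 128 only (100 + 28) |

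On schedule the last DB dose and the first OL dose share Day 168, and the DB rule keeps that day. For a continuing subject 167 of 168 OL days are then captured, and the loss is 1/168 = 0.6% of OL days.

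A gap can also open before the visit. If the last DB dose is Day 161 and OL starts on Day 168, Days 162 to 168 are lost: 168 − 161 = 7 days, including the Week 24 visit day. An interruption that ends before Week 24 opens no gap, because the last DB dose then comes later.

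With a missing response, status is judged against the first OL dose. Most of the gap closes. Only the first OL dose date stays unassigned, because the SAP does not say on which side it falls.

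If onset times were used instead of dates, and doses are assumed at 08:00 and 20:00, about 12 hours would be lost on Day 168 and about 12 on Day 336.

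**Partial dates.** Suppose OL starts on 15 June and an event on 20 June is recorded only as June. It is imputed to 1 June, which is before the last DB dose, so it becomes a DB TEAE. The exposed days run from OL start to the end of that calendar month. With starts spread evenly over a 30-day month this averages (0 + 1 + … + 29)/30 = 14.5, or about 15 days, and 15/168 = 8.9%. This is a share of OL days. The documents do not give the number of partial dates.

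**Adjoining periods.** With DB through the first OL dose date, and OL from the next day through Day 336, no day from 1 to 336 is lost when OL starts on time or 1, 3 or 7 days late.

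**The case against.** The strongest reply is that little is lost. On schedule there is no DB/OL gap. An event that prompts an interruption will usually have begun on or before the last dose taken, and so counts as DB. The 28-day tail keeps the Month 12 day for anyone whose last dose on study is in OL. The tables are descriptive, with no hypothesis tests. All of this stands and sets the size of the point.

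A second reply is that SAP Section 1 leaves Month 12 to 18 to an amendment, which could pick up the Month 12 day. Permanent loss is therefore not shown. But SAP 5.3 says that all planned Month 12 analyses are in this SAP, and an amendment that copied the strict lower bound would miss the day again.

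A reader might infer that events vanish from every safety output. They do not. SAP 11.2.2 provides a separate SAE listing. Laboratory and ECG results have their own by-visit tables, and the Month 12 window in Table 4 runs to the first dose date of the next period. The exposure-adjusted rates in SAP 11.2.5 are not stated by period, so they might count such events and then disagree with the frequency tables.

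On partial dates, a reader might take one month in six (28/168, about 17%) as the exposure. That would need every subject to start OL at the beginning of a calendar month. It is also fair to say that any rule is a convention: a day-missing event may truly be DB, and imputing it to OL start can err the other way.

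**Conclusion.** The point holds as a wording defect of small size. For a continuing subject the OL table loses one onset date, normally the Month 12 visit day. Any gap between the last DB dose date and a later first OL dose date is lost as well, for events with a response of Yes. Day +28 after the final dose is treatment-emergent by the general definition but in no period table. Up to about 9% of OL days are exposed to assignment to DB if the onset day is missing.

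This rests on onset being compared by date, on dosing at the scheduled visits, and, for the 9%, on OL starts being spread evenly within months. The 0.6% is a share of calendar time; the share of events may be higher because findings are dated to visits, but the documents give no figure for this.

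The documents do not support the reading that every Month 12 day event is dropped, or that all subjects have a gap at Week 24. No efficacy analysis is affected.

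**What to change.** Rewrite the period rules in SAP 11.2 so that they adjoin by date, in line with Table 4:

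- **DB TEAE:** onset from the first DB dose through the first OL dose date inclusive; if there is no OL dose, on or before last dose + 28 days.
- **OL TEAE:** onset after the first OL dose date through the first dose date of the Month 12 to 18 period inclusive; if the last dose on study is in OL, on or before last dose + 28 days.
- **Missing response:** use the same bounds.
- **Month 12 to 18 amendment:** start after that period's first dose date.

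The inclusive upper bounds matter. Ending DB before the first OL dose would, by date, move Week 24 visit findings made before any OL drug into OL. Ending OL before the next period's first dose would still exclude the Month 12 day if that dose is taken the same evening. The price is that an event arising on the Week 24 evening, after the first OL dose, counts as DB. The SAP should state that convention.

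In SAP 6.8.1, add that an onset with only the day missing, in the month and year of OL start, is assigned to the first day counted as OL unless other information shows onset before OL start. State the downside: some true DB events may be assigned to OL.

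The cost is a few sentences in two sections, with no new data. It should be settled before the database lock for the tables concerned.

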### **11.2.1. Adverse Events Resulting in Discontinuation from Study Drug**

The number and percentage of subjects with a TEAE resulting in study drug discontinuation will be presented by PT within SOC (presented in the same method as the analogous primary TEAE table) by treatment group. More than one AE can contribute to study drug discontinuation per subject. The first line of each table will display the number and percentage of subjects with at least one TEAE leading to study drug discontinuation. This summary will be produced for the DB period and OL period separately.

A listing of TEAEs resulting in premature study drug discontinuation will be provided, which will include subject ID, treatment period, treatment group, study day of the discontinuation, and other relevant information from the AE eCRF.

### **11.2.2. Deaths and Other Serious Adverse Events**

Summary tables of treatment-emergent serious adverse events (SAEs) will be presented. The number and percentage of subjects with an SAE will be presented by PT within SOC (each sorted in alphabetical order) by treatment group. The first line of the table will display the number and percentage of subjects with at least one SAE. This table will be produced for the DB period and the OL period separately.

Separate listings of SAEs and fatal TEAEs will also be provided. Each listing will include subject ID, treatment period, treatment group, study day of the SAE or fatal TEAE, and any additional relevant information from the AE eCRF.

### **11.2.3. Adverse Events of Acute Adrenal Insufficiency**

In addition to the TEAE summaries described above, adverse events of acute adrenal insufficiency will be presented in a table by PT and treatment group. This table will be produced for the DB period and the OL period separately.

The following PT (MedDRA, version 26.0) will be used to identify AEs of acute adrenal insufficiency/adrenal crisis:

- adrenocortical insufficiency acute

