## 4.6. Safety

Safety endpoints in the DB and OL periods include:

- Occurrence of treatment-emergent adverse events (TEAEs), treatment-emergent serious adverse events (TESAEs), adrenal insufficiency TEAEs, and TEAEs leading to discontinuation from study
- Observed and changes from baseline in clinical laboratory test values (including hematology, clinical chemistry, plasma renin activity [PRA], and coagulation)
- Observed and changes from baseline in vital sign values
- Observed and changes from baseline in 12-lead electrocardiogram (ECG) intervals
- Observed and changes from baseline in total scores from the Brief Psychiatric Rating Scale (BPRS)
- “Yes” responses to suicidal behavior or ideation at postbaseline assessments from the Columbia-Suicide Severity Rating Scale (C-SSRS)

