#### **7.4.2. CAH Medical History**

CAH medical history at study entry will be summarized by DB treatment group and overall using descriptive statistics. For conditions that are sex-specific, the denominator will be based on the number of subjects of that sex within the treatment group.

- CAH history assessments include:
- Age at CAH diagnosis
- How the CAH diagnosis was made
- Lifetime total number of adrenal crises (requiring hospitalization and parenteral glucocorticoid administration)
- Number of (lifetime) adrenal crises related to stopped/decreased glucocorticoid medication
- Causes of adrenal crises
- Number of adrenal crises within the past 10 years (requiring hospitalization and parenteral glucocorticoid administration)
- Number of adrenal crises within the past 10 years related to stopped/decreased glucocorticoid medication
- Number of adrenal crises within the past 5 years (requiring hospitalization and parenteral glucocorticoid administration)
- Number of adrenal crises within the past 5 years related to stopped/decreased glucocorticoid medication
- Number of adrenal crises within the past year (requiring hospitalization and parenteral glucocorticoid administration)
- Number of adrenal crises within the past year related to stopped/decreased glucocorticoid medication
- Age at menarche (female subjects only)
- Menstrual cycles occurring every 21-35 days (Y/N; female subjects of childbearing potential only not on hormonal or IUD contraception)

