### **11.2.4. Adverse Events Leading to Glucocorticoid Stress Dosing**

The number and percentage of subjects with a TEAE leading to glucocorticoid stress dosing will be presented by PT within SOC (presented in the same method as the analogous primary TEAE table) by treatment group. The first line of each table will display the number and percentage of subjects with at least one TEAE leading to glucocorticoid stress dosing. This summary will be produced for the DB period and OL period separately.

An overall summary table will be provided that summarizes the maximum severity of glucocorticoid stress dosing based on the following categories (in order of least to most severe):

- Oral dosing (alone, without parenteral dosing/ER visit/SAE)
- Parenteral dosing (without ER visit/SAE)
- ER visit without SAE (requiring glucocorticoid stress dosing)
- SAE (requiring glucocorticoid stress dosing)

Each subject will be counted once by their maximum severity of illness requiring glucocorticoid stress dosing. This table will be produced for the DB period and the OL period separately.

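### SAP 4.6 names adrenal insufficiency TEAEs as a safety endpoint, but SAP 11.2.3 tabulates only one acute preferred term, so no table gives the number of subjects per arm with the named endpoint

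*SAP*

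**What the plan says.** SAP 4.6 sets out the safety endpoints for the DB and OL periods. Among the occurrence endpoints it names "adrenal insufficiency TEAEs, and TEAEs leading to discontinuation from study". The word acute does not appear.

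SAP 11.2.3 is the only section that takes up this endpoint by name, and its scope is narrower: "adverse events of acute adrenal insufficiency will be presented in a table by PT and treatment group", separately for the two periods. The retrieval rule reads "The following PT (MedDRA, version 26.0) will be used to identify AEs of acute adrenal insufficiency/adrenal crisis", and the list that follows has one entry, "adrenocortical insufficiency acute". No wider term list, standardised query or clinical rule is given for insufficiency that is not acute.

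Other parts of the SAP pick up related events:

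- Section 11.2 has frequency tables of all TEAEs by system organ class and preferred term.
- Sections 11.2.1 and 11.2.2 do the same for TEAEs leading to study drug discontinuation and for SAEs.
- Section 11.2.4 tabulates TEAEs that led to glucocorticoid stress dosing and adds a severity table in which "Each subject will be counted once by their maximum severity of illness requiring glucocorticoid stress dosing".
- Section 11.2.5 gives exposure-adjusted incidence by preferred term.
- Section 11.4 counts orthostatic hypotension at each visit.

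**The concern.** The endpoint and its analysis do not have the same scope. The trial takes subjects on more than 13 mg/m²/day and aims for 8 to 10 mg/m²/day (protocol 8.1 and 9.3.1). Protocol 9.6.1 asks investigators to watch for any evidence of glucocorticoid insufficiency during reduction, not only for crisis. Protocol 11.1 has the investigator's diagnosis recorded as the event in place of its signs and symptoms, so whether a case reaches the 11.2.3 table depends on how that diagnosis is worded and coded.

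A reader who goes to 11.2.3 for the answer to the 4.6 endpoint could see a small or empty row while some cases sit under other terms. Because the endpoint bears on the safety of the dose reduction that the primary endpoint rewards, the subject count per arm should be available directly, not pieced together.

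**Working it through.** The point rests on text. There is no stated figure to reproduce.

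**Step 1: scope.** The endpoint in 4.6 is adrenal insufficiency, unqualified. The analysis in 11.2.3 is acute adrenal insufficiency or crisis, found through one preferred term. The second is a subset of the first.

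**Step 2: can the missing total be recovered from other tables?**

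- *General TEAE, discontinuation and SAE tables (11.2, 11.2.1, 11.2.2).* These count unique subjects within each preferred term. If k relevant terms have subject counts a₁, …, aₖ in one arm, the number of subjects with any of them lies between max(aᵢ) and Σaᵢ. The tables do not say where, because one subject can appear in several rows. The system organ class row also includes unrelated terms.
- *Stress-dosing tables (11.2.4).* These count any TEAE that led to stress dosing, whatever the illness. They can also miss insufficiency: protocol Section 7 describes a return to the previously tolerated dose when listed signs appear during reduction, and that is not stress dosing.
- *Exposure-adjusted rates (11.2.5).* These are again by preferred term.

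So each case is visible somewhere, but the subject-level total for the named endpoint is not.

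**Step 3: does the plan group terms elsewhere?** Yes. SAP 6.10 uses a standardised MedDRA query to identify COVID-19 cases.

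**Step 4: illustration on assumed values.** The documents give no event rate and no share of cases coded to the acute term. Assume a true subject rate p of 2% to 10% and a share s of 50% to 100%, with independent subjects and the planned 110 crinecerfont subjects (SAP 3.3).

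Expected subjects in the 11.2.3 row = 110 × p × s. Chance of an empty row = (1 − p × s)^110.

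| p | s | Expected subjects | Chance of empty row |
|---|---|---|---|
| 2% | 100% | 2.2 | 11% |
| 2% | 75% | 1.65 | 19% |
| 2% | 50% | 1.1 | 33% |
| 5% | 100% | 5.5 | 0.4% |
| 5% | 75% | 4.1 | 1.5% |
| 5% | 50% | 2.75 | 6.2% |
| 10% | 100% | 11 | <0.1% |
| 10% | 75% | 8.25 | <0.1% |
| 10% | 50% | 5.5 | 0.4% |

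Worked line: p = 5%, s = 50% gives 110 × 0.05 × 0.5 = 2.75 and (1 − 0.025)^110 = 0.062. At s = 100% the row is complete. The table shows only that, when events are rare, a few cases coded elsewhere can change how the row reads. It does not estimate what will happen.

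**The case against.** The strongest reply is that nothing is hidden. An event coded without the acute qualifier gets its own subject count per arm and period in the general tables, and again in the SAE, discontinuation, stress-dosing and exposure-adjusted tables where it qualifies. SAP 11.2.3 itself says that its table supplements those summaries. Orthostatic hypotension and clinical chemistry are summarised as well, and protocol 9.6.1 has the data monitoring committee review events needing sick-day dosing. Safety is descriptive, with no hypothesis tests. Adding the word acute to 4.6 would also remove the inconsistency.

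Much of this stands. What is missing is one pooled subject-level count, not the events themselves. Renaming the endpoint would make the sections agree, but only by narrowing what is reported.

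Three stronger readings are tempting, and the documents do not support them:

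- *That the risk is under-counted, or the comparison between arms distorted.* No document shows how cases will be coded, and nothing suggests that coding would differ between blinded arms. Protocol 9.6.1 describes crisis as an inherent risk of the disease and rates the likelihood of insufficiency at the target doses as low. It does not call this the main risk.
- *That on-study events cannot be compared with the crisis history in SAP 7.4.2.* That section counts "Lifetime total number of adrenal crises (requiring hospitalization and parenteral glucocorticoid administration") and similar items as descriptive history at entry. No planned analysis sets them against on-study events.
- *That crises by the 7.4.2 definition can be counted from 11.2.4.* That definition is a crisis diagnosis with a severity qualifier. The qualifier alone would also take in other hospitalised illness with parenteral cover. The SAE category in 11.2.4 shows neither route nor hospitalisation.

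**Conclusion.** The concern holds as a mismatch between a named endpoint and its analysis. As written, the SAP produces no per-arm count of subjects with any adrenal insufficiency TEAE, and the one dedicated table can understate that count. The size of any understatement cannot be given: it runs from none, if all cases code to the acute term, upward with the share coded elsewhere. This assumes that some insufficiency events could be coded to another term, which is plausible from the reporting rule in protocol 11.1 but is not shown by the documents. The primary and key secondary analyses are unaffected. This is an inexpensive improvement to safety reporting and should be made.

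**What to change.** In SAP 11.2.3, before the Week 24 database lock and unblinding of the sponsor:

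1. List by name the MedDRA 26.0 preferred terms that denote adrenal, adrenocortical or glucocorticoid insufficiency, acute or not, and adrenal crisis. Whether borderline terms such as steroid withdrawal belong is a clinical grouping choice, to be settled while blinded.
2. Report one row with the count and percentage of subjects having at least one TEAE in that group, per arm, separately for the DB and OL periods.
3. Keep the present acute term as its own subset row, with the other listed terms below it.
4. Refer to this table from 4.6 so that endpoint and analysis carry the same name.

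The cost is SAP wording and one extended table. The displayed rate may be somewhat higher because milder events enter the group, but the acute subset row keeps the narrower figure visible. If the sponsor intends only acute events, the minimum is to say so in 4.6. That restores consistency but leaves non-acute insufficiency without a total.
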